BLA Filing analysis is planned to be performed on all subjects dosed using data cutoff of 11 Feb 2021, for at least 12-month median follow-up duration (counting from time of the first dose to data cutoff date) and 6-month follow-up on confirmed objective responses (counting from the start of the last objective response to data cutoff date). All subjects dosed will be used in safety analysis and all subjects dosed with measurable disease at baseline (per IERC) will be used for efficacy analysis.

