4.3. FINAL ANALYSIS AND REPORTING

The final analysis will be performed after study completion and it will supplement the BLA Filing analysis.

All final planned analyses per protocol and this analysis plan must be performed after either locking records for relevant subjects or visits included in the analysis or the full database lock. See [Section 7](#) for discussion of requirements for data freeze, locking, and source data verification in the context of the COVID-19 pandemic.

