5.4. DEFINITION OF AN EXTENDED ON-TREATMENT PERIOD

Extended on-treatment period (follow-up) is defined as the time from the first dose of study treatment through 90 days after the last dose of study treatment or end of study, whichever occurs first. This is used for reporting immune-related AEs and also as a sensitivity analysis for reporting all treatment emergent adverse events.

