5.6. HANDLING OF PARTIAL DATES FOR ADVERSE EVENTS

When determining TEAEs, partial dates will be handled as follows.

- If the day of the month is missing, the onset day will be set to the first day of the month unless it is the same month and year as study treatment. In this case, the onset date will be assumed to be the first dose date of treatment.

- If the onset day and month are both missing, the day and month will be assumed to be 1 January, unless the event occurred in the same year as the study treatment. In this case, the event onset will be coded to the first dose date of treatment to conservatively report the event as treatment emergent.
- A missing onset date will be coded as the first dose date of treatment. If the resulting onset date is after a reported date of resolution, the onset date will be set equal to the date of resolution.
- A partially missing resolution date will be conservatively imputed as the latest date in the range of missing date element(s) (for example 2020-10-31 if the date is 2020-10-UNK), date of last dose + 90 days, day of study discontinuation, or death, whichever comes first.

Data listings will present the partial date as recorded in the electronic case report form (eCRF).

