7.4. SUBJECTS DISPOSITION

Subject disposition will be summarized including

- Number of subjects treated
- Number of subjects dosed at least 12 months before data cutoff
- Median time and range (in months) from first dose until data cutoff
- Number of subjects who completed study treatment as per protocol
- Number of subjects with treatment ongoing at the time of analysis
- Number of subjects who discontinued treatment and primary reasons of discontinuation (with “Progression of disease (compared to baseline)” listed as “Progressive disease”).
- Number of subjects who completed the study as per protocol
- Number of subjects ongoing on study
- Number of subjects who discontinued study and primary reasons of discontinuation

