The median duration of TEAE (in days) will be calculated using Kaplan Meier analysis for all patients and AE included in a cluster. Unresolved AEs or AEs with missing resolution information and date will be treated as censored data with the end of extended on-treatment period as censoring date.

Death summary table will present reasons for deaths on treatment period, in survival follow-up, and overall.

Death details will also be listed (if applicable) including:

- Number of doses of balstilimab
- Number of cycles

- Age at death
- Study days relative to first dose date, calculated as (death date – first dose date + 1)
- Number of days to death from last dose, calculated as (death date – last dose date + 1)
- Precipitating AE (if death is an outcome of AE)
- Immune-related AE (if death is an outcome of irAE per investigator)
- Cause of deaths

The following listings will be provided in Safety Analysis Set:

- All AEs (with TEAEs flagged)
- Related TEAEs
- Serious TEAEs
- TEAEs leading to treatment discontinuation
- TEAEs leading to death
- Death details (including age, study day, and days from last dose, AEs, and death cause).

Adverse events observed between signing the informed consent and first dose of study drug will be listed with negative study days.

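### The censoring rule for unresolved adverse events has no data-cutoff limit, so Kaplan-Meier AE durations in the filing analysis can include unobserved time

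*SAP*

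**What the plan says.** SAP 7.6.2 sets the estimator for each cluster of immune-mediated events: "The median duration of TEAE (in days) will be calculated using Kaplan Meier analysis for all patients and AE included in a cluster". Events that are unresolved, or have no resolution information and date, "will be treated as censored data with the end of extended on-treatment period as censoring date".

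SAP 5.4 defines that period as running from first dose "through 90 days after the last dose of study treatment or end of study, whichever occurs first".

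The timing comes from three other places:

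- SAP 4.2: "BLA Filing analysis is planned to be performed on all subjects dosed using data cutoff of 11 Feb 2021".
- SAP 4.3: "The final analysis will be performed after study completion and it will supplement the BLA Filing analysis". The filing cutoff is therefore not the end of the study.
- SAP 7.4 lists, among the disposition counts, "Number of subjects with treatment ongoing at the time of analysis", and also subjects ongoing on study. The plan expects such subjects but gives no number.

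SAP 5.6 limits an imputed partial resolution date to the latest date the partial date allows, "date of last dose + 90 days, day of study discontinuation, or death, whichever comes first". It does not name the data cutoff either.

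**The concern.** A censoring date tells Kaplan-Meier that the event was seen to be unresolved up to that day. If the date lies after the data cutoff, that is not known: the event may have resolved the day after cutoff. The event stays in the risk set with no chance of being recorded as resolved, so the estimated resolution rate falls and the curve rises.

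The SAP avoids this for its efficacy times. In SAP 3.5, overall survival is censored at the date last known alive as of the cutoff. In SAP 7.7.3 and 7.7.9, duration of response and PFS are censored no later than the last evaluable assessment. AE duration is tied instead to a date calculated forward from last dose.

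At stake is the reported duration of immune-mediated events, overall and for grade 3 or higher, in the analysis that supports the regulatory filing.

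**Working it through.** The documents state no AE duration, event count or number of subjects ongoing at cutoff, so there is no figure of the plan's own to reproduce. The check is date arithmetic, then the direction of the effect, then an illustration of its size.

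**1. Who is affected**

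Literal censoring date = min(last dose + 90 days, end of study). SAP 5.4 does not say whether end of study means the subject's or the trial's. Protocol 3.5 places end of trial 24 months after the last subject's last planned dose. On either reading it has not occurred for a subject still on study at the cutoff, so last dose + 90 days applies.

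11 Feb 2021 − 90 days = 13 Nov 2020. A last dose after that day puts the censoring date past the cutoff. With g = days from last dose to cutoff, the overshoot is 90 − g:

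| g (days) | Overshoot (days) | Literal censoring date |
|---|---|---|
| 0 | 90 | 12 May 2021 |
| 14 (dosing interval, SAP 7.6.1) | 76 | 28 Apr 2021 |
| 42 | 48 | 31 Mar 2021 |

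A subject on schedule at cutoff is thus credited with 76 to 90 unobserved days.

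**2. Direction**

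At each resolution time the Kaplan-Meier factor is 1 − d/n, where d is the number resolving and n the number at risk. Moving a censoring date later leaves every d unchanged and can only raise n or leave it alone. Every factor, and so the curve, rises or stays the same.

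Six invented events show this. Five resolve at days 10, 20, 60, 100 and 120. One is unresolved at day 40, when the cutoff falls; the literal rule moves its censoring to day 40 + 90 = 130.

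| Day | Curve, censored at cutoff | Curve, literal rule |
|---|---|---|
| 10 | 5/6 = 0.833 | 5/6 = 0.833 |
| 20 | 0.833 × 4/5 = 0.667 | 0.833 × 4/5 = 0.667 |
| 60 | 0.667 × 2/3 = 0.444 | 0.667 × 3/4 = 0.500 |
| 100 | 0.444 × 1/2 = 0.222 | 0.500 × 2/3 = 0.333 |
| 120 | 0 | 0.333 × 1/2 = 0.167 |

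The curve is higher from day 60 on. If the median is the first time the curve reaches 0.5 or less, it is 60 days under both rules. A convention that takes the midpoint of a flat stretch at exactly 0.5 would give (60 + 100)/2 = 80 under the literal rule. In a small cluster the median may or may not move.

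**3. Illustrative size**

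Assumptions, none from the documents: 100,000 AEs per case; exponential durations; a share f of AEs in subjects on drug at cutoff; onset-to-cutoff time uniform on 0–365 days for those AEs; their last dose 0–14 days before cutoff; all other AEs censored at a uniform 0–365 days under both rules. Each cell gives the median with the cutoff limit, then under the literal rule.

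| True median (days) | f = 10% | f = 30% | f = 50% |
|---|---|---|---|
| 30 | 29.9 → 30.1 (+0.6%) | 29.8 → 30.3 (+1.7%) | 30.2 → 31.1 (+2.8%) |
| 60 | 59.9 → 60.6 (+1.3%) | 59.8 → 61.9 (+3.5%) | 60.3 → 64.1 (+6.4%) |
| 120 | 120.0 → 123.0 (+2.5%) | 120.9 → 129.4 (+7.0%) | 121.0 → 136.6 (+12.9%) |
| 240 | 241.8 → 250.9 (+3.8%) | 241.0 → 271.0 (+12.5%) | 239.7 → 292.1 (+21.8%) |

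Percentages use unrounded medians.

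Further runs varied the gap between end of accrual and cutoff as well as the share ongoing:

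- 30 days read 30 to 31.5: 31.5/30 = 1.05.
- 60 days read 60 to 65: 65/60 = 1.083, or about 9% allowing for rounding of the 65.
- 180 days read 187 to 218: 187/180 = 1.039 and 218/180 = 1.211.

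**The case against.** The strongest reply is that this is silence, not an instruction. The filing analysis is run on data to 11 Feb 2021, SAP 7.6.2 does not tell anyone to count days after that, and a programmer may cap at the cutoff without being told. That is possible. But the rule gives a specific date, and followed as written it yields dates after the cutoff. A rule that is right only if not followed literally should be corrected.

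Four other limits on the point stand:

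- A reader might infer that every unresolved event is censored at last dose + 90 days. SAP 5.4 also stops at end of study. On the natural subject-level reading, those who died or left are already limited.
- A reader might infer that SAP 5.6 already holds a better rule that 7.6.2 failed to use. SAP 5.6 does name death and discontinuation, but it also lacks the cutoff, so on this point it has the same gap.
- The effect is largely confined to the analysis made before study completion. A small residue could remain in the final analysis, because Protocol 7.2.1 ends AE reporting at the start of new anticancer treatment when that precedes 90 days after last dose.
- SAP 7.6.2 reports the percentage resolved beside the duration for each cluster, so a reader can see how much is unresolved. That helps interpretation but does not correct the estimate.

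**Conclusion.** The point holds, as a minor one. In the filing analysis the stated rule allows up to 90 unobserved days per unresolved event, for subjects still on study and last dosed after 13 Nov 2020. The bias can only be upward or nil.

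A stronger conclusion, that the reported durations will be materially too long, is tempting but not supported. It depends on the number of subjects ongoing, when accrual stopped, and how long the events last, and the documents do not give these. In the assumed scenarios the shift in the median is negligible to about 5% for 30-day events, about 0–9% for 60-day events and about 4–21% for 180-day events. Short events are hardly affected; long-lasting ones are the most exposed. These ranges are illustrations, not estimates for this trial.

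Duration of treatment-emergent events is a listed secondary endpoint (SAP 3.5), but the summary is descriptive and SAP 7.1 plans no formal hypothesis testing. The primary endpoint, confirmed ORR, is unaffected.

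**What to change.** In SAP 7.6.2, censor unresolved AEs at the earliest of:

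- last dose + 90 days;
- end of study for that subject (death, discontinuation or last contact);
- the data cutoff of the analysis.

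Add the data cutoff to the limits on imputed partial resolution dates in SAP 5.6. Stating that end of study is the subject's own also removes any confusion with the trial-level definition in Protocol 3.5.

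The cost is one clause in each of two SAP sections and the matching line of programming. No new data are needed. Results change only for events whose literal censoring date, or imputed resolution date, falls after the new limit.

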#### **6.3.3.2. Safety Follow-up Visit**

The mandatory Safety Follow-Up Visit should be conducted for all subjects approximately 4 weeks after the last dose of study drug or before the initiation of a new antineoplastic treatment, whichever comes first. Subjects with an AE of Grade >1 will be further followed until the resolution of the AE to Grade 0-1 or until beginning of a new antineoplastic therapy, whichever occurs first. Subjects with an adverse drug reaction (ADR) ongoing at the Safety Follow-up Visit must be followed up until the ADR resolves, becomes stable, or is considered not clinically significant by the investigator.

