### 7.2.1. Definition of the Adverse Event Reporting Period

The AE reporting period for safety surveillance begins when the subject provides written consent and continues until either 90 days after the last dose of study drug or the start of new anticancer treatment, whichever comes first. Following the End-of-Treatment Safety Follow-up Visit, only treatment-related AEs will be documented through the Treatment Follow-up Period of up to 12 months after the last dose of study drug or until disease progression and/or initiation of a new line of therapy, whichever comes first.

Any SAE suspected to be related to trial treatment must be reported whenever it occurs, irrespective of time elapsed since last dose of study drug.

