5.10. HANDLING OF MISSING DATA

Missing data will not be imputed, except for:

- Missing date parts, i.e., partial dates, discussed above
- Missing AEs grade severity and relationship to study drug of AEs, discussed in [Section 7.6.2](#)
- Missing efficacy assessments discussed in Section 7.7.

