The analysis of irAEs in the above summaries will be performed using data as reported by investigator (the primary analysis). In addition, as an exploratory analysis, TEAEs using sponsor's broad and narrow definitions of irAEs, will be summarized. For each irAE, the summary will include median time (and range) to onset, median duration (and range) of the first instance of such AE per patient. Finally, descriptive statistics will be provided for time of onset, cycle of onset, and cumulative dose at onset of first irAE of any type.

If an SOC or PT was reported more than once for a subject, the subject would only be counted once in the incidence for that SOC or PT.

In tabulation by severity grade:

- For a given SOC, only the most severe SOC for each subject will be included
- For a given PT, only the most severe PT for each subject will be included

In addition, TEAEs (evaluated within extended treatment period) will be reported for the following clusters of immune-mediated AEs: pneumonitis, colitis and diarrhea, hepatitis, and liver function abnormalities, endocrinopathies, nephritis and renal dysfunction, skin disorders, other immune-related AEs. These clusters will be defined by the following MedDRA version 22.1 Preferred Terms:

- **Pneumonitis:** interstitial lung disease; pneumonitis; acute interstitial pneumonitis; immune-mediated pneumonitis
- **Colitis:** allergic colitis, autoimmune colitis, colitis, colitis erosive, colitis microscopic, enterocolitis hemorrhagic, eosinophilic colitis, necrotizing colitis, neutropenic colitis, enterocolitis, immune-mediated enterocolitis,
- **Diarrhea:** diarrhoea, diarrhoea hemorrhagic
- **Hepatitis:** acute hepatic failure, autoimmune hepatitis, hepatic failure, hepatitis, hepatitis acute, hepatotoxicity, liver injury, hepatocellular injury, immune-mediated hepatitis, immune-mediated hepatic disorder, drug-induced liver injury
- **Hypothyroidism:** autoimmune hypothyroidism, hypothyroid goiter, hypothyroidism, immune-mediated hypothyroidism, myxoedema, thyroid atrophy
- **Hyperthyroidism:** Basedow's disease, hyperthyroidism, Marine Lenhart syndrome, primary hyperthyroidism, immune-mediated hyperthyroidism, secondary hyperthyroidism, tertiary hyperthyroidism, thyroid dermatopathy, thyroid crisis, thyrotoxic periodic paralysis, toxic goiter, toxic nodular goiter,

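### Cluster AE durations: unresolved events are censored at last dose + 90 days but fully dated later resolutions are not truncated there, so the Kaplan-Meier median can be biased short

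*SAP*

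**What the plan says.** **Estimator.** SAP 7.6.2: "The median duration of TEAE (in days) will be calculated using Kaplan Meier analysis for all patients and AE included in a cluster".

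**Censoring.** The next sentence of SAP 7.6.2 deals with events that are unresolved, or whose resolution information and date are missing. They "will be treated as censored data with the end of extended on-treatment period as censoring date". SAP 5.4 runs that period "through 90 days after the last dose of study treatment or end of study, whichever occurs first".

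**Partly missing resolution dates.** SAP 5.6 imputes these as the latest date the known parts allow, subject to a cap: "date of last dose + 90 days, day of study discontinuation, or death, whichever comes first". The result is still a resolution date, so the event counts as resolved.

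**Complete resolution dates after the cut-off.** Nothing is said. SAP 5.10 opens with "Missing data will not be imputed, except for" and lists partial dates, missing AE grade or relationship, and missing efficacy assessments. None of these alters a complete resolution date.

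**Which events enter.** SAP 7.6.2: "TEAEs (evaluated within extended treatment period) will be reported for the following clusters of immune-mediated AEs".

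**Follow-up after the cut-off.** Under Protocol 6.3.3.2, a subject with a drug reaction ongoing at the Safety Follow-up Visit "must be followed up until the ADR resolves, becomes stable, or is considered not clinically significant by the investigator". Protocol 7.3 follows ongoing SAEs until they stabilise or the outcome is known. Protocol 7.2.1 adds that after that visit "only treatment-related AEs will be documented through the Treatment Follow-up Period of up to 12 months after the last dose of study drug", ending sooner at progression or a new line of therapy.

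**Beside the median.** SAP 7.6.2 also tabulates the percentage resolved in each cluster.

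**The concern.** Kaplan-Meier needs censoring that does not depend on what happens next. Take two events, both open 90 days after last dose and both followed further. One resolves at day 200 with a full date and contributes its whole duration. The other is still ongoing at day 200 and is cut back to day 90. Whether an event stays in the risk set beyond the cut-off then depends on its later outcome. Past that point the risk set holds only events already known to resolve, and the curve is pulled down.

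The clusters most exposed are those where events may persist, such as hypothyroidism, pituitary-adrenal insufficiency and diabetes. There the table could print a finite median duration when most events remain unresolved. Duration of TEAEs is a listed secondary endpoint (SAP 3.5), and these tables would go into the BLA filing analysis (SAP 4.2).

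**Working it through.** The documents give no AE duration figure, so there is nothing to reproduce. The estimator is S(t) = product over resolution times of (1 − d/n), with d the resolutions at that time and n the events still at risk. The median is the first t with S(t) ≤ 0.5. Durations are plain date differences; the SAP 7.2 convention adds one day to each and changes no comparison.

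Three rules are compared:
- **A, as worded:** complete resolution dates count as recorded; unresolved events are censored at last dose + 90.
- **B, truncate all:** any event not resolved by last dose + 90 is censored there.
- **C, last known status:** resolutions count as recorded; unresolved events are censored when last seen.

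**Case 1 (assumed inputs).** There are 20 events, each starting 60 days before last dose. Two resolve 200 days after last dose and 18 are ongoing at 365 days.
- The cut-off falls at a duration of 60 + 90 = 150 days, the late resolutions at 60 + 200 = 260, and last follow-up at 60 + 365 = 425.
- A: 18 are censored at 150, leaving n = 2 at 260. S = 1 − 2/2 = 0, so the median is **260 days**.
- B: all 20 are censored at 150. S stays at 1, so the median is **not reached**.
- C: n = 20 at 260. S = 1 − 2/20 = 0.90, so the median is **not reached**.

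With one late resolution and 19 ongoing, rule A still gives S = 1 − 1/1 = 0 at that time. With no late resolutions, A and B are identical. The late resolutions therefore drive the result.

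Suppose instead that the two late resolution dates lacked the day, with no earlier death or discontinuation. SAP 5.6 would place both at 150 days as resolutions. S = 1 − 2/20 = 0.90 and the median is not reached. The same histories give different medians depending on how completely the date was entered.

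**Case 2 (assumed inputs).** There are 10 events with the cut-off at 120 days' duration. Resolutions occur at 20, 40, 60, 200, 250 and 300 days, and four events never resolve. All rules give S = 0.9, 0.8, 0.7 at the first three.
- A: n = 3 at 200, so S = 0.7 × 2/3 = 0.47 and the median is 200 days; the curve then falls to 0.
- B: the curve stays at 0.70 and the median is not reached.
- C: S = 0.7 × 6/7 = 0.60, then 0.50 at 250 and 0.40 at 300. The median is 250 days.

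**Simulation (assumed inputs).** There are 200,000 events per scenario. Onset is uniform from 180 days before to 90 days after last dose, resolving events have exponential durations, and status is known to 365 days after last dose. Selected median durations in days:

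| Never resolve | Median of resolvers | A | B | C |
|---|---|---|---|---|
| 0% | 30 | 30 | 30 | 30 |
| 0% | 90 | 88 | 90 | 90 |
| 0% | 180 | 156 | 179 | 180 |
| 30% | 30 | 51 | 55 | 54 |
| 30% | 90 | 134 | 162 | 162 |
| 50% | 90 | 198 | not reached | not reached |
| 70% | 90 | 271 | not reached | not reached |

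The bias is negligible for short events that all resolve. It appears when resolution is slow and grows with the share that persists.

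**The case against.** **The SAP never says that late dates count as recorded.** This stands: it is inferred from silence. SAP 7.6.2 evaluates cluster events within the extended period and SAP 5.6 caps partial dates at last dose + 90, so a common day-90 horizon may be intended. Under that reading the bias disappears. But the first text governs which events enter, and the second covers only incomplete dates and turns them into resolutions, not censored times. The censoring sentence does not reach a fully dated late resolution, so a programmer following it would use the recorded date.

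**Follow-up past day 90 is narrow.** This also stands. Documentation is limited to treatment-related events and stops at progression or new therapy. Under Protocol Table 13, footnotes 1 and 2, such subjects have the 3-month visit and then telephone survival contact. Reaction follow-up may end once the event is stable. Late resolutions may be few.

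**The inputs are assumed.** They are, and the simulation gives every event follow-up to day 365, which favours a large effect. The SAP plans only the median here, so the proportion unresolved at one year is not a planned output and is not relied on.

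**Persistent events are not hidden.** A reader might infer that the analysis makes lasting toxicity look resolved. The documents do not support that: unresolved events are censored, and the percentage resolved is tabulated for the same cluster. That column reveals persistence but does not correct the median beside it.

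**The reach is limited.** The rule governs an additional cluster summary. Investigator-reported irAEs, the primary irAE analysis, have their own median duration of first instance.

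**Conclusion.** The point holds in a limited form. Applied as worded, SAP 7.6.2 uses one horizon for unresolved events and none for fully dated resolutions, which makes censoring depend on outcome and biases the cluster median short. The bias needs both persistent events and some complete resolution dates after the cut-off. In the assumed 20-event case it turns a median that is not reached into 260 days; for short events that all resolve it is negligible.

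It would go too far to say that the SAP prescribes counting late resolutions at their real dates, or to quote a size for this trial. The first rests on silence. The second needs the number of resolutions after the cut-off, which the documents do not give.

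Severity is minor to moderate: a descriptive safety summary may mislead, and the primary endpoint is unaffected.

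**What to change.** State one horizon for both outcomes in SAP 7.6.2.

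- **Simplest, needing no new data:** censor every event not resolved by the end of the extended on-treatment period at that date, including events that resolve later.
- **Alternative:** count every resolution at its recorded date, and censor unresolved events at the last date their status is known, no later than death, end of study or data cutoff. The documents do not show a field holding that last date, so check that it can be derived before choosing this.

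Align the partial-date rule in SAP 5.6 with the choice. Under the first option, a resolution whose known date parts place it after the cut-off should be censored there, not counted as resolved there. Under the second, the cap at last dose + 90 should not apply to durations.

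The cost is one sentence and one derivation. Some medians will become longer or not reached.
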